5.3 Definition of Dose-Limiting Toxicity

The safety of this approach will be confirmed by assessing toxicity potentially attributable to the daily progesterone treatment. National Cancer Institute Common Terminology Criteria for Adverse events version 5.0 (NCI CTCAE v. 5.0) will be used for all grading. A dose limiting toxicity (DLT) is defined as an adverse event or abnormal laboratory value assessed as grade 3 or greater that is not clearly due to the underlying disease or extraneous causes with the following exceptions:

- Grade 3 nausea/vomiting or diarrhea for less than 72 hours with adequate antiemetic and other supportive care.
- Grade 3 fatigue for greater than 1 week.
- Grade 3 or higher electrolyte abnormality that lasts up to 72 hours, is not clinically complicated, and resolves spontaneously or responds to conventional medical interventions.
- Grade 3 or higher amylase or lipase that is not associated with symptoms or clinical manifestations of pancreatitis.
- Grade 3 neutropenia.
- Grade 3 thrombocytopenia without clinically significant bleeding.

For the Dose Finding Phase of the study, the dose will be deemed tolerable if no DLTs occurs within the first 4 weeks of progesterone treatment. Prior to enrolling patients into a higher dose level, CTCAE grade ≥ 2 adverse events will be reviewed for all patients at the current dose level.

Management and dose modifications associated with adverse events are outlined in **Section 5.4**.

Dose escalation will proceed to different dose levels according to the scheme presented earlier (**Section 5.2**).

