5.2 Dosing and Administration

Formulation: An aqueous formulation of natural progesterone complexed with 2-hydroxypropyl- β -cyclodextrin (Subcutaneous progesterone; IBSA Institut Biochimique SA, Lugano, Switzerland) will be used. An IND for this formulation will be cleared by the FDA and cross-referenced to support the present study.

Route of administration: Each dose (25-75 mg) will be given daily by subcutaneous injection using a tuberculin syringe with sterile technique. The site of injection will rotate along different sites (standard locations including abdomen, thigh) based on patient preference with at least 1 day break between reinjection of a particular site. Each injection will consist of 25-50 mg of drug in 1-2 ml with multiple injections to be used if higher doses of drug are called for per study.

Timing of administration: Drug will be injected subcutaneously at about same time in the AM \pm 3 hours each day.

Pharmacokinetic assessment (only 1st 3 patients at each dose cohort): Will only be done on the first three patients at each dose level cohort. Assessment time points will be start on day 1 of treatment. Blood draws will be performed immediately prior to drug administration (by subcutaneous injection). Subsequent blood samples will be obtained at 30 minutes, 1 hour, 2 hours, 4 hours, 6 hours and 8 hours following progesterone injection. One additional time point will be performed on day 8 just prior to drug injection on those days.

Dose Finding Phase (Part 1):

Patients will be enrolled sequentially and will follow a 3+3 design. The dose levels that will be potentially used are on the following table:

Dose Level	Dose of aqueous natural progesterone for injection (mg)
Level -1	25
Level 0	50
Level 1	75

Dosing will start at Dose Level 0 and will escalate or de-escalate according to the following rules:

Dose Level -1

- 0 of 3 with DLT → **expand Level -1 to 20 patients**
- 1 of 3 with DLT → 3 more at Level -1
 - 1-2 of 6 with DLT → **expand Level -1 to 20 patients**
 - 3-4 of 6 with DLT → consider stopping study
- 2-3 of 3 with DLT → consider stopping study

Dose Level 0

- 0 of 3 with DLT → move to Level 1
- 1 of 3 with DLT → 3 more at Level 0
 - 1 of 6 with DLT → move to Level 1
 - 2 of 6 with DLT → **expand Level 0 to 20 patients**

3-4 of 6 with DLT → drop to Level -1
2-3 of 3 with DLT → drop to Level -1

Dose Level 1

0 of 3 with DLT → **expand Level 1 to 20 patients**
1 of 3 with DLT → 3 more at Level 1

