1-2 of 6 with DLT → **expand Level 1 to 20 patients**
3-4 of 6 with DLT → **expand Level 0 to 20 patients**
2-3 of 3 with DLT → **expand Level 0 to 20 patients**

During the dose finding phase of the study, a treatment will be considered safe/tolerable if no DLT defined as \geq grade 3 toxicity during the first 4 weeks drug therapy not clearly due to the underlying disease or extraneous causes with exceptions as noted in **Section 5.3**. After treatment initiation of up to 6 patients at a dose level and continuation for a minimum of 4 weeks with AE assessment, enrollment to the next (higher or lower) dose level as determined by the rules will only start after data is presented to the Winship Data Safety Monitoring Committee (DSMC) and final approval is obtained for starting the next dose level.

Dose escalations will be reviewed by the Winship Data Safety Monitoring Committee (DSMC) (per Winship SOP 7.9 Dose Escalation Determinations for Sponsor-Investigator or Investigator Initiated Studies). The PI or designee will provide an update on all relevant safety data of patients entered to a dose level to the DSMC when dose escalation is planned. Upon obtaining approval from the DSMC, dose escalation can proceed.

Dose Expansion Phase (Part 2):

The purpose of cohort expansion is to gather additional safety and tolerability information, and evaluate the efficacy of aqueous natural progesterone for injection at the dose determined by the Dose Finding Phase of the study.

The PI or designee must provide the DSMC a report outlining the overall enrollment and path to decision for the escalation dose(s) selected.

Continuous evaluation of toxicity events in the cohort expansion will be performed throughout enrollment in the expansion cohort. If, at any time, the aggregate rate of treatment-related toxicities meeting DLT criteria exceeds 33% across all subjects treated in the expansion cohort, the findings will be discussed and further enrollment may be interrupted. Depending on the nature and grade of the toxicity and after assessing the risk:benefit ratio, a new dose(s) for all cohorts may be initiated at a previously tested lower dose level, or at a dose level intermediate to previously tested lower dose levels.

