5.4 Dose Modification

Progesterone will be withheld for any instance of a CTCAE v5.0 grade 3 or greater toxicity (except for grade 3 neutropenia or grade 3 thrombocytopenia without clinically significant bleeding). Drug may be resumed, at the discretion of the treating physician, if the toxicity has reduced to the grade 0-1 level within 14 days. Treatment will be discontinued if toxicity persists beyond 14 days. For toxicity not clearly due to the underlying disease or extraneous causes, 50% dose reduction of original dose will be used when resuming treatment after sufficient recovery of toxicity as defined above. If toxicity is clearly due to the underlying disease or extraneous causes, no dose reduction is required after sufficient recovery of toxicity as defined above. Treatment will also discontinue if there is development of a DLT after one dose reduction.

Progesterone will be discontinued if patient develops any specific contraindication for use of progesterone (e.g. thromboembolic event). The treating physician can also stop progesterone if he/she feels that doing so would be in the best interest of the patient.

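### Section 5.3 exempts grade 3 fatigue lasting more than 1 week from the DLT definition, the reverse of the other two time-limited exceptions

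*Combined protocol and SAP*

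**What the plan says.** Section 5.3 counts as a DLT any adverse event or laboratory abnormality of grade 3 or higher, unless it is clearly due to the disease or an extraneous cause (called attributable below), and then removes six exceptions. Three of the six carry a duration:

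- For gastrointestinal toxicity, the exempt event is "Grade 3 nausea/vomiting or diarrhea for less than 72 hours with adequate antiemetic and other supportive care".
- For fatigue, the exempt event is "Grade 3 fatigue for greater than 1 week".
- For electrolytes, the exempt event is "Grade 3 or higher electrolyte abnormality that lasts up to 72 hours", subject to further conditions about complications and resolution.

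Section 5.2 and Section 15.1 both define DLTs for dose finding by pointing to the Section 5.3 exceptions. Neither restates the fatigue rule.

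The definition is used in three places:

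- **The 3+3 rules in Section 5.2.** At Level 0 (50 mg), 0 of 3 leads to Level 1 (75 mg), while "2-3 of 3 with DLT → drop to Level -1" (25 mg).
- **The expansion-phase trigger in Sections 5.2 and 15.1.** If DLTs exceed 33%, "the findings will be discussed and further enrollment may be interrupted".
- **The individual stopping rule in Section 5.4.** "Treatment will also discontinue if there is development of a DLT after one dose reduction".

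**The concern.** An exception removes an event from the DLT count. Exempting fatigue of more than 1 week therefore removes the worse event and leaves the milder one in. The neighbouring bullets work the other way: gastrointestinal toxicity and electrolyte disturbance are forgiven only when short. The plan gives no reason for treating long fatigue as more acceptable than short fatigue.

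Safety and tolerability form a primary objective, and Section 15.1 sets the maximum tolerated dose from the 3+3 count. A site that follows the text exactly would score this event backwards. Counting brief fatigue only makes the trial more cautious. The worry is that prolonged fatigue is not counted.

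Fatigue is also plausible here. Section 13 lists it as a common reaction to the subcutaneous product (at least 1 in 100, fewer than 1 in 10, grade not stated). Section 3.2 names it among the effects that limit the oral dose, although it ties those to first-pass metabolites, which may matter less by injection.

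**Working it through.** No sample size, power or error rate in the plan depends on this bullet, so there is no stated figure to reproduce. The check has two parts.

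**1. Reading the list**

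| Exception with a duration | Exempt (not a DLT) | Counted as a DLT |
|---|---|---|
| Nausea/vomiting or diarrhea, grade 3 | under 72 hours | 72 hours or more |
| Electrolytes, grade 3 or higher | up to 72 hours, if the other conditions hold | longer |
| Fatigue, grade 3, as written | over 1 week | 1 week or less |

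Two exempt the short event and one exempts the long event.

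**2. Effect on the dose rules**

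*Worked case.* Suppose two or three of the first three patients at 50 mg have 10 days of attributable grade 3 fatigue within the first 4 weeks, and there are no other DLTs.

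- As written: 0/3, so the cohort qualifies for 75 mg.
- With the bullet reversed: 2/3 or 3/3, so the rule is to drop to 25 mg.

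*Probabilities at Level 0.* Let p be the chance that a patient has a counted DLT. From the Section 5.2 rules:

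- Escalate (0/3, or 1/3 then 0/3): E = (1−p)³ + 3p(1−p)² × (1−p)³
- Expand Level 0 (1/3 then 1/3): X = [3p(1−p)²]²
- Drop to Level −1 (all other outcomes): D = 1 − E − X

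Assumed, because the documents give no rates: other DLTs occur in 5% of patients; prolonged grade 3 fatigue occurs in a fraction f, independently; there is no brief grade 3 fatigue. As written, p = 0.05. Corrected, p = 1 − 0.95 × (1 − f).

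For p = 0.05: E = 0.857 + 0.135 × 0.857 = 0.973; X = 0.135² = 0.018; D = 0.008.

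| Wording | f | p | Escalate | Expand Level 0 | Drop |
|---|---|---|---|---|---|
| As written | any | 0.0500 | 0.973 | 0.018 | 0.008 |
| Corrected | 1% | 0.0595 | 0.963 | 0.025 | 0.012 |
| Corrected | 2% | 0.0690 | 0.952 | 0.032 | 0.016 |
| Corrected | 5% | 0.0975 | 0.910 | 0.057 | 0.033 |
| Corrected | 10% | 0.1450 | 0.824 | 0.101 | 0.075 |

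With other DLTs at 10% instead, the chance of escalating is 0.906 as written and, at f = 10% (p = 1 − 0.90 × 0.90 = 0.19), 0.730 corrected.

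**The case against.** The wording and its placement are hard to dispute. The case on the other side is that little harm would follow.

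- **Patients are protected without the DLT label.** Section 5.4 holds drug for grade 3 fatigue of any duration. It allows resumption only after recovery to grade 0–1 within 14 days, at half dose if the event is attributable, and otherwise ends treatment. This stands. For one patient, the bullet matters mainly for the rule on a DLT after dose reduction.
- **Dose moves are not automatic.** A new level opens only after DSMC presentation and when "final approval is obtained for starting the next dose level". Before a higher level, grade 2 or worse "adverse events will be reviewed for all patients at the current dose level". Prolonged fatigue would be seen. This stands too, but the committee would still receive a DLT tally that is wrong for this event. In addition, Section 12 replaces treated patients who stop with under 28 days of drug. A patient stopped early for fatigue persisting beyond 14 days could be replaced without ever scoring a DLT.
- **The illustration looks in one direction only.** It sets brief grade 3 fatigue to zero, yet brief fatigue counts as written. If brief and prolonged fatigue each occurred in 2%, p would be 1 − 0.95 × 0.98 = 0.069 under both wordings and the chance of escalating would be the same. This is correct. In that case the error lies in which patients are counted.
- **The higher rates lack support.** Section 13 puts fatigue of any grade below 10%, so a 10% rate of prolonged grade 3 fatigue is above that range, and 5% would need more than half of all fatigue to be severe and long. The Section 13 data are from women in the product's pivotal trial, so higher rates cannot be excluded, but nothing in the documents supports them. Section 4.1 gives a half-life of 13 to 18 hours. Taking five half-lives as washout (65 to 90 hours, about 3 to 4 days), drug-caused fatigue lasting over a week after a hold may be uncommon.
- **The intent is not stated.** The bullet could be a DLT criterion placed in the wrong list. On that reading, too, prolonged fatigue should count.

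**Conclusion.** The concern holds. As written, Section 5.3 excludes attributable grade 3 fatigue of more than 1 week from the DLT count and includes shorter fatigue, and no other section corrects this. That miscounts the quantity that sets the dose in a dose-finding trial.

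The practical size is unknown, because the documents give no grade 3 fatigue rate. Under the stated assumptions, the chance of qualifying to escalate is overstated by 0.010 at a 1% rate (0.973 against 0.963) and by 0.149 at 10% (0.973 against 0.824). The chance of a drop to 25 mg is 0.008 as written, against 0.012 and 0.075. The effect is small at low rates, and the 5% and 10% rows should be read as stress cases. The conclusion rests on the reversed definition, not on these probabilities. The safeguards reduce the consequences, and the 33% trigger is in any case discretionary.

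**What to change.** Reword the Section 5.3 bullet so that it exempts grade 3 fatigue lasting less than (or up to) 1 week. The sponsor's clinicians should confirm the duration and say how exactly 7 days is treated. Sections 5.2 and 15.1 need no edit, because they cite 5.3 without repeating the fatigue text.

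If any grade 3 fatigue has already been recorded, re-check its DLT status in both directions before the next DSMC dose decision. The documents show none.

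The cost is a one-bullet wording amendment, with no change to sample size, schedule or analysis.

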5.4 Dose Modification

Progesterone will be withheld for any instance of a CTCAE v5.0 grade 3 or greater toxicity (except for grade 3 neutropenia or grade 3 thrombocytopenia without clinically significant bleeding). Drug may be resumed, at the discretion of the treating physician, if the toxicity has reduced to the grade 0-1 level within 14 days. Treatment will be discontinued if toxicity persists beyond 14 days. For toxicity not clearly due to the underlying disease or extraneous causes, 50% dose reduction of original dose will be used when resuming treatment after sufficient recovery of toxicity as defined above. If toxicity is clearly due to the underlying disease or extraneous causes, no dose reduction is required after sufficient recovery of toxicity as defined above. Treatment will also discontinue if there is development of a DLT after one dose reduction.

Progesterone will be discontinued if patient develops any specific contraindication for use of progesterone (e.g. thromboembolic event). The treating physician can also stop progesterone if he/she feels that doing so would be in the best interest of the patient.

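### The 3+3 tally takes no account of dose received: a patient held and halved for a DLT-exempt event still counts as DLT-free at the full level

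*Combined protocol and SAP*

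**What the plan says.** **What counts as a DLT.** Section 5.3 defines a DLT by event and grade and lists six exceptions. One is "Grade 3 nausea/vomiting or diarrhea for less than 72 hours with adequate antiemetic and other supportive care". The others are fatigue, short-lived electrolyte abnormalities, amylase or lipase rises without pancreatitis, grade 3 neutropenia, and grade 3 thrombocytopenia without significant bleeding.

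**What happens to the patient's dose.** Section 5.4: "Progesterone will be withheld for any instance of a CTCAE v5.0 grade 3 or greater toxicity". Only the neutropenia and thrombocytopenia exceptions are carried over. Drug may restart, at the physician's discretion, if the toxicity falls to grade 0-1 within 14 days. Unless disease or another cause is clearly responsible, "50% dose reduction of original dose will be used when resuming treatment after sufficient recovery of toxicity as defined above".

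**How the level is judged.** Section 5.3: "the dose will be deemed tolerable if no DLTs occurs within the first 4 weeks of progesterone treatment". The escalation rules in 5.2, to which 15.1 refers, use only the number of patients with a DLT. Section 15.1 defines a safety and an efficacy population, but no DLT-evaluable one. Section 12 replaces treated patients only if they withdraw or are discontinued with less than 28 days of drug.

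**Safeguards.** Adverse events of grade 2 or more are reviewed "Prior to enrolling patients into a higher dose level". Section 5.2 also requires that data go to the DSMC and that "final approval is obtained for starting the next dose level". For the expansion phase, the PI or designee "must provide the DSMC a report outlining the overall enrollment and path to decision for the escalation dose(s) selected". During expansion, enrollment may be interrupted if DLT-type toxicity exceeds 33%.

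**The concern.** Two rules, each reasonable alone, leave a gap where they meet. Four of the six exempt event types do not count against the dose level, yet they force a hold and, if drug is resumed, a half dose. The realistic ones are brief gastrointestinal events and fatigue: amylase and lipase are not on the schedule of assessments, and the metabolic panel falls only at baseline and day 29 in the DLT window.

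A Level 0 patient who is halved takes 25 mg, which is the Level -1 dose. In the tally that patient is still a DLT-free observation at 50 mg and supports a move to 75 mg. Cohorts have three to six patients, so one such case is a large share of the evidence. The error runs in one direction, towards escalation or expansion. What is at stake is the dose that 15.1 calls the MTD and carries into Part 2.

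**Working it through.** **1. Dose received by one such patient.** Inputs: 28-day window (15.1), hold of up to 14 days and 50% resumption (5.4). Share of planned dose = (full-dose days + 0.5 × half-dose days) / 28.

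| Hold starts | Hold | Full-dose days | Half-dose days | Share of planned dose |
|---|---|---|---|---|
| Day 2 | 14 d | 1 | 13 | 7.5/28 = 27% |
| Day 8 | 14 d | 7 | 7 | 10.5/28 = 37.5% |
| Day 8 | 3 d | 7 | 18 | 16/28 = 57% |
| Day 15 | 14 d | 14 | 0 | 14/28 = 50% |
| Day 15 | 3 d | 14 | 11 | 19.5/28 = 70% |

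The half-life in 4.1 is 13-18 h. Seven daily doses span at least 168/18 = 9.3 half-lives, so a day-8 patient was near steady state before the event. What is lost is time at the full dose (21 of 28 days), not the peak level.

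**2. What 0 of 3 then rests on.** With one day-8, 3-day-hold patient, the cohort took (28 + 28 + 7)/84 = 75% of its doses at the full level. The exact one-sided 95% upper bound on the DLT rate is 1 − 0.05^(1/3) = 63% for 0 of 3. If that patient is not evaluable, it is 1 − 0.05^(1/2) = 78% for 0 of 2.

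**3. Effect on the decision, given one such patient among the first three.** Assumptions, none from the documents: true 28-day DLT risk p at full dose, constant daily hazard, no hazard off drug, half-dose hazard h times the full-dose hazard, and decisions made by the tally alone.

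- Reduced patient DLT-free: S = (1−p)^((7+18h)/28).
- No DLT in the first three: P0 = (1−p)²S. One DLT: P1 = 2p(1−p)S + (1−p)²(1−S).
- Move 50 to 75 mg = P0 + P1(1−p)³.
- Expand Level 1 = P0 + P1[(1−p)³ + 3p(1−p)²].

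For the reference case (all at full dose) S = 1−p. At p = 0.33:

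| Case | S | Move to 75 mg | Expand Level 1 |
|---|---|---|---|
| All at full dose | 0.670 | 0.434 | 0.632 |
| As written, h = 1 | 0.699 | 0.448 | 0.645 |
| As written, h = 0.5 | 0.795 | 0.491 | 0.688 |
| As written, h = 0 | 0.905 | 0.539 | 0.736 |

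At p = 0.20 the chance of moving up is 0.709 at full dose and 0.718, 0.747 and 0.778 as written. One case therefore adds about 1 to 10 percentage points.

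**4. Expected effect.** The documents give no rate for these events. If 2% to 5% of patients had one (an assumption), the chance of at least one in three patients is 1 − 0.98³ = 6% to 1 − 0.95³ = 14%. Multiplied by a shift of 1.3 to 10.5 points, the average is about 0.1 to 1.5 points.

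**5. Two possible remedies in the same model, p = 0.33.**

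- *Count the patient as a DLT.* Move to 75 mg = 0.67⁵ = 0.135. Expand Level 1 = 0.67² × (0.67³ + 3 × 0.33 × 0.67²) = 0.449 × 0.745 = 0.335.
- *Replace the patient if no DLT occurred.* S becomes S(1−p): 0.606, 0.533 and 0.469 for h = 0, 0.5 and 1. Move to 75 mg = 0.406, 0.373 and 0.344. Expand Level 1 = 0.604, 0.571 and 0.543.

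**The case against.** **The review steps would catch it.** A grade 3 event with a hold and a halved dose falls within the grade 2+ review, and the tally alone does not authorize a move to another level. This stands in part: the probabilities above assume that the tally decides, so they are upper-end illustrations. But no text tells the DSMC how to count such a patient. The review and approval wording also concerns a move to another level. With 0 of 3 at Level 1 the next step is expansion at the same level, for which 5.2 asks for a report.

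**Part 2 has a backstop.** The 33% toxicity rule could interrupt enrollment or lower the dose. This is a real mitigation. It acts after patients have been exposed and does not correct the Part 1 count.

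**Section 5.2 already has exposure wording.** It reads "After treatment initiation of up to 6 patients at a dose level and continuation for a minimum of 4 weeks with AE assessment". This can be read as four weeks at the level. It is ambiguous: it names no dose, and a patient who is held and then halved has arguably continued.

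**Stronger readings that the documents do not support.** A reader might infer that 5.3 and 5.4 contradict each other. They do not: one judges a level, the other protects a patient, and staff can follow both. A reader might also infer that the trial will select an unsafe dose. Nothing shows this. Section 13 lists nausea, vomiting and fatigue at 1% to under 10% each, for any grade and in a different population, so grade 3 cases are probably uncommon.

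**Conclusion.** The gap is real and specific. Followed as written, the 3+3 rules can credit a level with a DLT-free patient who took about 27% to 70% of the planned dose in the cases worked above.

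Given one day-8, 3-day-hold case among the first three patients and a 33% DLT risk, the chance of moving to 75 mg is 0.448 to 0.539 instead of 0.434, and of expanding Level 1 is 0.645 to 0.736 instead of 0.632. The top values need a half-dose hazard of zero. All of them assume that the case has occurred and that the tally alone decides. Averaged over how often such a case is likely, the effect is small.

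It would also be too strong to say that 20 further patients depend on the choice. The 20 include the three or six dose-finding patients at that level, so 20 − 6 = 14 to 20 − 3 = 17 would be newly exposed, and fewer if the futility rule stops enrollment.

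This is a flaw in a counting rule that serves a primary objective, not evidence of harm. It is worth closing because the change is cheap and should be settled before a cohort decision turns on it.

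**What to change.** Add to 5.2 and 15.1, for the 3+3 count only:

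- A patient is DLT-evaluable if he or she had a DLT, or took a prespecified minimum of planned doses at the assigned level in the first 28 days (for example 75%, that is 21 of 28).
- A patient who falls short without a DLT, including one held and halved for an event exempt under 5.3, is replaced for the count and stays in the safety population.
- Each such patient is reported to the DSMC with the reason before any decision to escalate or expand.

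Do not automatically count an exempt event as a DLT. In the affected cohort that would cut the chance of moving up from 0.434 to 0.135, and of expanding Level 1 from 0.632 to 0.335, and it would undo the exemptions in 5.3.

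**Cost.** No new data are needed: the drug diary, the eCRF and the action-taken field of the adverse event record already capture doses and interruptions. The price is an occasional extra dose-finding patient. At the planned 1-2 patients per month that is about 2-4 weeks to enroll plus 4 weeks of observation. Replacement also leans slightly towards caution, because a DLT always counts while a DLT-free short exposure is repeated. In the affected cohort at 33% risk, the chance of moving up becomes 0.344 to 0.406, against 0.434 with everyone at full dose.

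### An attributable forced stop below grade 3 under the Section 5.4 contraindication rule is not counted in the 3+3 tally, so a dose can pass at 0 of 3 although a patient had to come off drug

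*Combined protocol and SAP*

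**What the plan says.** **Discontinuation.** Section 5.4: "Progesterone will be discontinued if patient develops any specific contraindication for use of progesterone (e.g. thromboembolic event". No grade is stated. Section 12 lists the same reason for withdrawal, again without a grade.

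**What counts as a DLT.** Section 5.3: "A dose limiting toxicity (DLT) is defined as an adverse event or abnormal laboratory value assessed as grade 3 or greater", with attribution wording and a short list of exceptions. Section 15.1 repeats the threshold and sets a 28-day window. Neither section makes a forced permanent stop a DLT.

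**Consequence of a zero count.** Section 5.3: "the dose will be deemed tolerable if no DLTs occurs within the first 4 weeks of progesterone treatment". Under Section 5.2, 0 of 3 at Level 0 moves the trial to Level 1, and 0 of 3 at Level 1 expands Level 1 to 20. Level -1 works the same way ("expand Level -1 to 20 patients").

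**Replacement.** Section 12 replaces treated patients who leave with less than 28 days of drug. It makes no exception for toxicity and does not mention the 3+3 tally.

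**Expansion.** The 33% rule in Sections 5.2 and 15.1 counts only treatment-related toxicities that meet DLT criteria.

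**Reviews.** Before a higher level opens, grade 2 or higher "adverse events will be reviewed for all patients at the current dose level" (Section 5.3). In Section 5.2, "enrollment to the next (higher or lower) dose level as determined by the rules will only start after data is presented" to the DSMC and "final approval is obtained for starting the next dose level". For the expansion, Section 5.2 says: "The PI or designee must provide the DSMC a report outlining the overall enrollment and path to decision for the escalation dose(s) selected". Section 16 adds monthly study-team meetings that review toxicity.

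**The concern.** Part 1 is meant to find the highest dose that patients can safely tolerate. A patient who must stop permanently within four weeks because of an event attributed to the drug has not tolerated that dose in any ordinary sense. Yet if the event is below grade 3, the count that drives the decision does not move. If the patient is also replaced, the tally can end up holding three patients without an event.

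At stake is the caution built into the 3+3. One counted event in three calls for three more patients before the trial goes up a level or commits to 20 patients at that dose. An uncounted forced stop skips this step.

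**Working it through.** **1. The plan's own figure.** Section 15.1 gives 6 to 12 patients for dose finding. Under the Section 5.2 rules, Level 0 takes 3 or 6 patients, and a second level, if reached, takes 3 or 6. The smallest total is 3 + 3 = 6 (or 6 at Level 0 with 2 DLTs, which expands Level 0 directly). The largest is 6 + 6 = 12. The figure reproduces and is not in dispute.

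**2. The rules side by side.** Suppose one of the first three patients has an attributable forced stop below grade 3 within 28 days, and there is no other DLT.

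| Level | As written | If the stop counted |
|---|---|---|
| Level 0 | 0 of 3: move to Level 1 | 1 of 3: 3 more at Level 0 |
| Level 1 | 0 of 3: expand Level 1 to 20 | 1 of 3: 3 more at Level 1 |

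The as-written column is the same if the patient is replaced and the replacement has no DLT. This step needs no rates.

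**3. Illustrative size.** The documents give no rate for such stops, no grade split and no DLT rate, so these inputs are assumptions:
- d = 0.10, the chance of any other DLT in 28 days
- u = 0.01 or 0.05, the 28-day chance of an attributable forced stop below grade 3 that the fix would count, independent of other DLTs

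The chance of leaving Level 0 for Level 1 (0 of 3, or 1 of 3 followed by 0 of 3), when each patient counts with probability p, is

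U(p) = (1 − p)³ + 3p(1 − p)⁵

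The three ways of handling the stopped patient give:
- **Stop counted:** p = 1 − (1 − d)(1 − u)
- **Not counted, patient replaced:** p = d / (1 − (1 − d)u)
- **Not counted, patient kept as a non-DLT:** p = d

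| u | p, counted | U, counted | p, replaced | U, replaced | p, kept | U, kept | Gap, replaced | Gap, kept |
|---|---|---|---|---|---|---|---|---|
| 0.01 | 0.1090 | 0.8910 | 0.1009 | 0.9047 | 0.10 | 0.9061 | 1.37 points | 1.52 points |
| 0.05 | 0.1450 | 0.8238 | 0.1047 | 0.8983 | 0.10 | 0.9061 | 7.45 points | 8.24 points |

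**4. Sensitivity to d.** With the stopped patient kept as a non-DLT, the gap at u = 0.01 is 1.73 points for d = 0.15 and 1.74 for d = 0.20. At u = 0.05 it is 8.90 and 8.71. The figures in step 3 are therefore not upper bounds. If u = 0, the gap is zero.

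**5. More than one stop.** The chance of two or more such stops in three patients is 3u²(1 − u) + u³. This is 0.03% at u = 0.01 and 0.7% at u = 0.05. The realistic case is a single stop.

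**The case against.** The strongest reply is that the gap may never open. It needs a contraindication event that is below grade 3, falls within 28 days and is attributable. The documents do not say how thromboembolic events are graded, give no rate for them, and exclude patients with active or recent (six-month) thromboembolic disease. The Section 13 adverse-reaction table lists no such event, although it describes women in the pivotal trial and not glioblastoma patients. This stands: frequency is unknown and may be near zero.

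Second, the event would probably be seen. The grade 2 review, DSMC approval of the next level and the monthly toxicity meetings all bear on it. This largely stands, but none of them says how the event should count. The grade 2 review is tied to opening a higher level. DSMC approval is worded for the next level up or down, and for the expansion Section 5.2 names only a report, so approval does not clearly cover expanding the level just tested.

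Third, the grade 3 threshold is a legitimate design choice, and nothing shows these events to be dose-related. Calling a grade 1 event a DLT while uncomplicated grade 3 neutropenia is exempt would be hard to defend. That is a fair reason to set the fix at grade 2 or higher.

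A reader might infer that patients are left on a contraindicated drug, or that such events disappear from the safety data. Neither is so: Section 5.4 stops the drug, and the safety population in Section 15.1 keeps every treated patient.

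**Conclusion.** The gap holds on the plain text. Followed exactly, the rules can deem a dose tolerable and expand it at 0 of 3 after an attributable forced stop below grade 3, without the three further patients that one counted event would bring. This conclusion reads Section 5.4 as having no grade limit, because none is stated.

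The size is uncertain. The 1.4 to 1.5 and 7.5 to 8.2 point differences rest on an assumed 10% other-DLT rate and assumed stop rates of 1% and 5%. They are illustrations, neither bounds nor forecasts. No sample-size, alpha or power figure changes.

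A reader might go further and infer that the selected dose is likely to be unsafe, or that the 33% rule fails as a stopping rule. The documents support neither. They give no rate from which to judge the dose, and crossing 33% leads only to discussion and possible interruption of enrolment. The point is a cheap improvement of low to moderate weight.

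**What to change.** - **Sections 5.3 and 15.1:** also count as a DLT any grade 2 or higher event in the first 28 days that forces permanent discontinuation under the Section 5.4 contraindication rule, subject to the attribution wording already in Section 5.3.
- **Section 12:** state that such a patient stays in the 3+3 tally as a DLT, even if replaced for other purposes.
- **Expansion:** the 33% rule already refers to DLT criteria, so it would follow the new definition.

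The cost is wording. Discontinuation reason, event grade and attribution are already recorded. The price in conduct is slightly more conservative escalation and possibly 3 more patients at a level.
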